SPARSE is a single-center observational study aiming to investigate if suPAR measured preoperatively and immediately after surgery can predict the risk of future complications and post-operative mortality in adults following major non-cardiac surgery.

METHODS

Design

This is a prospective observational study designed in accordance with the declaration of Helsinki. The study will be register at Clinical Trials.gov and has been approved by the Institutional Review Board of the University Hospital of Larisa, under the reference number 60580/11-12-2018.

Patient eligibility

Consecutive patients who are scheduled to undergo elective major non-cardiac surgery with expected duration ≥ 2 hours under general anesthesia will be screened for

inclusion. All operative approaches will be eligible for inclusion, including open, laparoscopic and robotic procedures. Patients fulfilling the following inclusion criteria will be included: age \geq 18 years, and American Society of Anesthesiologists' (ASA) physical status I to IV.

Exclusion criteria will be age <18 years, any infection within the previous 4 weeks, severe liver disease, patients on renal replacement therapy pre-operatively, patients who had previously received a transplant, patients with allergies, inflammatory or immune system disorders, and/or connective tissue disease including rheumatoid arthritis, ankylosing spondylitis, and systemic lupus erythematosus, administration of steroid, antipsychotic, or anti-inflammatory/immunomodulatory medication during the 3 months prior to surgery, administration of opioids during the past week, asthma, obesity ($BMI \geq 30 \text{ kg m}^{-2}$), mental disability or severe psychiatric disease, alcohol or other abuse, legal incapacity or limited legal capacity, and subjects within the exclusion period of another study.

Management of Anesthesia and Surgical Procedures

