Endotracheal intubation and anesthetic care will be performed according to our institutional routine. Intravenous induction of general anaesthesia will include midazolam 0.15-0.35 mg/kg iv over 20-30 seconds, fentanyl 1 μ g/kg, propofol 1.5-2 mg/kg, ketamine 0.2 mg/kg (intravenous bolus), and rocuronium 0.6 mg/kg. All drugs will be prepared in labelled syringes and induction will be achieved by administration of a predetermined iv bolus dose on the basis of the patient's weight and/or age. Laryngoscopy and intubation will proceed in a standard fashion, while the position of the endotracheal tube will be confirmed by auscultation and

capnography/capnometry. The patients will then connected to an automated ventilator (Draeger Primus®; Drägerwerk AG & Co., Lübeck, Germany).

All patients will be ventilated using a lung-protective strategy with tidal volume of 7 mL/kg, positive end-expiratory pressure of 6-8 cmH₂O, plateau pressures <30 cmH₂O, and recruitment maneuvers repeated every 30 min after tracheal intubation.⁴⁴ Maintenance of general anesthesia will include desflurane 1.0 MAC with 40% oxygen and 60% air, while intraoperative dose changes will be left to the anesthesiologist in charge of the patient. Depth of anesthesia (bispectral index-BIS, Covidien, France) will be monitored, with the target ranging between 40 and 60.^{45,46} Normocapnia will be maintained by adjusting the respiratory rate as needed, while normothermia (37°C) will be maintained throughout the intraoperative period.

All patients will be operated by at least two consultant surgeons who will be supervised by a Professor of Surgery.

Sampling and laboratory measurements

Participants will undergo sampling of peripheral venous blood, immediately after arrival to the OR, and at the Post-Anesthesia Care Unit (PACU). Blood samples drawn from all patients and EDTA plasma will be stored at -80° C until later measurement. Plasma suPAR levels will be determined using the suPARnostic® quick triage lateral flow assay (ViroGates, Denmark), according to the manufacturers instructions.

Microcirculation flow analysis

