In addition to routine hemodynamic data, sublingual microvascular flow will be measured using noninvasive technology. We will obtain measurements preoperatively (PRE), intraoperatively (INT), and postoperatively after arrival in the PACU (POST). At each time point, we will image the microcirculatory network of the sublingual mucosa with sidestream darkfield (SDF+) videomicroscopy which has an increased optical resolution resulting in one pixel recording an area of $0.56 \mu\text{m}^2$. This device uses the new SDF+ technology that allows the red blood cells to be visualised with greater accuracy and detail, which is essential for enhancing the capabilities of the analysis application.

We will use the sublingual space as the site of imaging because it shares the same embryologic origin as the splanchnic mucosa and can reflect derangements in splanchnic blood flow; impaired sublingual microcirculatory blood flow is associated with increased mortality and worsening organ failure in patients with sepsis.⁴⁷⁻⁵¹

Outcomes

The primary endpoint will be the presence of complications and/or admission to ICU and/or mortality within the first 60 postoperative days.

Secondary endpoints will be intraoperative complications (including desaturation [$\text{SpO}_2 <92\%$ for 3 minutes or more], need for unplanned recruitment maneuvers, hypotension [defined as systolic blood pressure $<90 \text{ mmHg}$ or mean arterial pressure $<65 \text{ mmHg}$ for 3 minutes or more or need of vasoactive drugs for correction], need for unplanned vasoactive drugs [need for vasoactive drugs not

planned before and/or continuous infusion], and/or acute new arrhythmia [atrial fibrillation, sustained ventricular tachycardia, supraventricular tachycardia, and/or cardiac arrest]), reintubation, hospital length of stay, and length of stay in ICU. Secondary endpoints will also include postoperative complications within 90 days after surgery defined as in the SURPAS studies,⁵²⁻⁵⁴ with the inclusion of atelectasis and ileus, resulting in 22 possible postoperative complications, as well as survival at hospital discharge, at 90 days, and at 1 year.

Data Collection and Monitoring

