Data analysis will be based on predefined data points on a prospective data collection form. The staff will be blinded to measurements until the end of the study and all data are analyzed. Clinical monitoring throughout the study will be performed to maximize protocol adherence, while an independent Data and Safety Monitoring research staff will monitor safety, ethical, and scientific aspects of the study. Data collection will include demographics, anesthesia parameters, C-reactive protein, P-POSSUM score, ACS-NSQIP score, APACHE II, SOFA, and the Charlson Age-Comorbidity Index (Charlson score).⁵⁵ We will use a SAS macro based on ICD-10 diagnoses to calculate the Charlson score.^{56,57} Two other simpler models adding predictive value to the ASA classification will be also used; the Surgical Mortality Probability Model and a similar model proposed by Glance and Donati.^{58,59}

Data management

The goal of the clinical data management plan is to provide high-quality data by adopting standardized procedures to minimize the number of errors and missing data, and consequently, to generate an accurate database for analysis. Remote monitoring is performed to signal early aberrant patterns, issues with consistency, credibility and other anomalies. Any missing and outlier data values are individually revised and completed or corrected whenever possible.

Sample size and predefined statistical analysis plan

Patients will be consecutively included during the study period, in a convenience sample and will be stratified into low-risk or high-risk groups, according to suPAR level (suPAR_{high} above and suPAR_{low} below 5.5 ng/ml), respectively.⁶⁰ An a priori power analysis was done set to detect a difference of 0.50 on the suPAR (between suPAR_{high} and suPAR_{low} group, based on the researchers' preference. The number of patients planned for recruitment was rounded up to 100 to allow for flexibility in the study. This sample size was estimated to achieve 80 percent power to detect the suggested difference. The sample size calculation was made using G*Power 3.1.⁶¹ The association between ASA classification, suPAR level, CRP and the rate of postoperative complications will be analyzed with logistic regression and Cox regression analyses, estimating odds ratios (ORs) and hazard ratios (HRs).

Ethics and dissemination

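### The postoperative suPAR sample and POST microcirculation measurement are tied to the PACU, so a patient sent straight from theatre to ICU, always a primary-endpoint event, has none scheduled

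*Combined protocol and SAP*

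**What the plan says.** The Aim names two predictors and defines the second by time: the study asks whether "suPAR measured preoperatively and immediately after surgery can predict the risk of future complications and post-operative mortality".

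The methods define it by place. Under Sampling and laboratory measurements: "Participants will undergo sampling of peripheral venous blood, immediately after arrival to the OR, and at the Post-Anesthesia Care Unit (PACU"). Under Microcirculation flow analysis: "We will obtain measurements preoperatively (PRE), intraoperatively (INT), and postoperatively after arrival in the PACU (POST"). Neither section gives a time window or another location.

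Under Outcomes: "The primary endpoint will be the presence of complications and/or admission to ICU and/or mortality within the first 60 postoperative days". ICU admission is not limited to unplanned or later admission.

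Patient eligibility takes elective major non-cardiac surgery expected to last at least 2 hours and "American Society of Anesthesiologists' (ASA) physical status I to IV", with no exclusion for planned ICU care. On missing values, Data management says only: "Any missing and outlier data values are individually revised and completed or corrected whenever possible".

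**The concern.** A patient taken directly from theatre to ICU never reaches the place where the second sample and the POST images are scheduled. The same transfer makes the patient a primary-endpoint event. Whether the postoperative predictor is available would then depend on the outcome it is meant to predict, and every patient lost this way would be an event.

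At stake is the postoperative half of the Aim: fewer events, wider intervals, an event rate that looks too low, and possibly a biased odds ratio. An undrawn sample cannot be recovered by a data query, so the gap has to be closed before sampling.

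Drawing the sample on ICU arrival without any further rule leaves a second problem. The ICU admission has then already happened and cannot be an outcome predicted by that sample.

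**Working it through.** The plan gives no figure on this point: no event rate, no share of direct ICU transfers and no suPAR distribution by outcome. The only documented input is the planned N of 100, used here simply as the total. Everything else below is assumed for illustration.

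**1. What the rule schedules**

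| Path after surgery | Preoperative suPAR | Postoperative suPAR and POST images | Primary endpoint |
|---|---|---|---|
| Theatre to PACU | scheduled | scheduled | event or no event |
| Theatre directly to ICU | scheduled | not scheduled | always an event |

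**2. Events and precision**

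Let E be the events in 100 patients and q the direct transfers without a sample. The analysis keeps E − q events among 100 − q patients. For a logistic slope, information is roughly N × p × (1 − p), which equals events × non-events / N, taking the spread of suPAR as unchanged. The standard error ratio is the square root of (information with all patients / information without the q patients).

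For E = 30, full information is 30 × 70 / 100 = 21.0.

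- q = 5: 25 × 70 / 95 = 18.4; ratio √(21.0/18.4) = 1.07; event rate 25/95 = 26.3%.
- q = 10: 20 × 70 / 90 = 15.6; ratio √(21.0/15.6) = 1.16; event rate 20/90 = 22.2%.

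Over a range of assumed event counts:

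| E | q | Share of events lost | Information, all → kept | SE ratio |
|---|---|---|---|---|
| 20 | 5 | 25% | 16.0 → 12.6 | 1.13 |
| 20 | 10 | 50% | 16.0 → 8.9 | 1.34 |
| 30 | 5 | 17% | 21.0 → 18.4 | 1.07 |
| 30 | 10 | 33% | 21.0 → 15.6 | 1.16 |
| 40 | 5 | 12.5% | 24.0 → 22.1 | 1.04 |
| 40 | 10 | 25% | 24.0 → 20.0 | 1.10 |

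**3. Direction of any bias**

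Take 30 events and 70 non-events, with q = 10. Assume postoperative suPAR above the plan's 5.5 ng/ml cut-off in 20% of non-events (14 high, 56 low) and 40% of the 20 other events (8 high, 12 low). With the direct-ICU patients missing, the odds ratio is (8 × 56)/(12 × 14) = 2.67. With them included, it depends on their own suPAR:

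| High suPAR among the 10 direct-ICU patients | All events, high/low | OR, all patients | OR, direct-ICU missing | Effect of the loss |
|---|---|---|---|---|
| 80% | 16/14 | (16 × 56)/(14 × 14) = 4.57 | 2.67 | towards the null |
| 40% (as other events) | 12/18 | (12 × 56)/(18 × 14) = 2.67 | 2.67 | none |
| 20% | 10/20 | (10 × 56)/(20 × 14) = 2.00 | 2.67 | away from the null |

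A continuous version agrees. Let x be suPAR in SD units, standard normal, with logit P(event) = −0.95 + ln(1.8) × x (about 29% events). Among events, let the log odds of direct transfer be linear in x, and refit the logistic model without those patients. The true OR is 1.80 per SD.

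| Slope of direct transfer on x, among events | OR, one sixth of events lost | OR, one third lost |
|---|---|---|
| +1.0 | 1.57 | 1.37 |
| +0.5 | 1.67 | 1.54 |
| 0 | 1.80 | 1.80 |
| −0.5 | 1.96 | 2.13 |

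Loss that depends on the outcome alone leaves the logistic odds ratio unchanged, as in case-control sampling. Bias needs a further link between suPAR and direct transfer among event patients.

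**The case against.** The strongest reply is that the protocol never describes a patient bypassing the PACU. The share could be zero at this single center. The text also points partly the other way: storage is described as "Blood samples drawn from all patients and EDTA plasma will be stored at -80° C until later measurement", and the Aim's timing suggests that everyone is meant to be sampled. This stands to the extent that a reader might infer direct-ICU patients will in fact go unmeasured. The documents show only that nothing is scheduled for them; staff may improvise. It does not close the gap. The storage sentence names no other place or time, and the Aim's timing is the part that the PACU rule cannot deliver for such patients.

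A second reply is that losing only events does not by itself bias an odds ratio. This stands in full, as step 3 shows. A reader might infer that the association must be pulled towards the null. That needs higher suPAR in direct-ICU patients than in other event patients. The Background makes it plausible, since it reports raised suPAR in critical illness, but the reverse could hold, for example if some ICU beds are booked by type of procedure.

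A third reply concerns scope, and it also stands. The preoperative sample and the PRE and INT images are untouched, and the hypothesis under the title concerns preoperative suPAR only. The plan specifies no comparison of preoperative with postoperative suPAR and no analysis of POST images, so harm to those analyses cannot be claimed.

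Finally, a sample on ICU arrival is not useless. It can still predict later complications and death, but not the admission that preceded it.

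**Conclusion.** The concern holds as a gap in the sampling rule that is tied to the outcome. The methods define by place what the Aim defines by time. Anyone who bypasses the PACU has no scheduled postoperative measurement and is, under the endpoint as written, an event.

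If such transfers occur and go unsampled, three consequences are certain for the postoperative suPAR analysis: fewer events, lower precision and an understated event rate. With 20 to 40 events per 100 and 5 or 10 direct transfers, 12.5% to 50% of events are lost and the standard error rises by about 4% to 34%. At 30 events the rise is about 7% or 16%. These sizes rest on assumed event counts and transfer numbers.

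Bias in the odds ratio is conditional, and its direction cannot be settled from the documents. Preoperative prediction of the primary endpoint stands. The change is worth making before sampling because it is cheap then and impossible afterwards.

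**What to change.** - In Sampling and laboratory measurements and in Microcirculation flow analysis, replace the PACU as the defining condition with a fixed window after the end of surgery, applied wherever the patient is, PACU or ICU. The sponsor should choose the window length.
- In the analysis plan, state that analyses of postoperative suPAR count only endpoint events that begin after the sample, so that a direct ICU transfer is not treated as predicted by a later sample. Later complications and deaths in these patients still count. Analyses of preoperative suPAR keep the full endpoint.
- Report the number of direct theatre-to-ICU transfers.

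The cost is protocol wording, one analysis rule and one reported count. The planned number of samples does not rise, but some blood samples and images must be taken in the ICU. The event count for postoperative suPAR will be slightly lower than for preoperative suPAR and should be reported as such.

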University of Thessaly, School of Health Sciences

Faculty of Medicine

Department of Anesthesiology

STUDY PROTOCOL

A Prospective Observational Study on Assessment of the Soluble Urokinase Plasminogen Activator Receptor in Adult Patients Undergoing Major Non-cardiac Surgery (SPARSE): Study protocol

(SPARSE: if our hypothesis is correct, the SuPAR will help to investigate whether the preoperative suPAR level can aid in identifying patients at high risk for postoperative complications, morbidity and mortality.)

BACKGROUND

Soluble urokinase plasminogen activator receptor

The biomarker soluble urokinase plasminogen activator receptor (suPAR) is the soluble form of the cell membrane-bound protein urokinase plasminogen activator receptor (uPAR), which is expressed mainly on immune cells, endothelial cells, and smooth muscle cells. uPAR is released during inflammation or immune activation, and therefore the suPAR level reflects the extent of immune activation in the individual.¹ All human beings have a baseline level of suPAR that is individually determined and increases with age. Studies have shown that the suPAR level is

associated with morbidity and mortality in a number of acute and chronic diseases and in the general population.²⁻¹⁵ The suPAR level is elevated across diseases, and not solely associated with one specific disease. Therefore, suPAR is applicable as a prognostic marker and not as a diagnostic marker. This characteristic may be utilized for risk stratification in unselected patients.

Originally, uPAR was proven a receptor for urokinase (uPA) which splits plasminogen into active plasmin. Moreover, uPAR interacts with other proteins and plays a role in several important cell processes like migration, adhesion, angiogenesis, proliferation, and chemotaxis.¹ The suPAR protein was discovered in 1991, when it was found to be a marker of cancer progression.¹ In recent years, several studies have shown that suPAR is associated with a number of chronic diseases (including cardiovascular, hepatic, renal, and pulmonary diseases), and that the level is a predictor of a negative outcome of various infectious diseases (tuberculosis, HIV, malaria, sepsis, meningitis, pneumonia) and in critically ill patients.^{2-12, 15,17-21}

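### The primary composite counts any ICU admission, so an ICU bed booked before elective surgery would score as an event even after an uneventful course

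*Combined protocol and SAP*

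**What the plan says.** The Outcomes section defines the primary endpoint in one sentence: "The primary endpoint will be the presence of complications and/or admission to ICU and/or mortality within the first 60 postoperative days". The components are joined so that any one of them is sufficient. No section narrows the ICU component by planning status, indication or minimum stay.

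Other text that bears on the point:

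- The Aim is to find out whether suPAR "can predict the risk of future complications and post-operative mortality". It does not mention ICU use.
- Patient eligibility covers elective major non-cardiac surgery in ASA classes I to IV.
- The Outcomes section separates planned from unplanned care elsewhere. One intraoperative secondary endpoint is "need for unplanned vasoactive drugs", and recruitment manoeuvres are qualified in the same way.
- The Background says that everyone has a "baseline level of suPAR that is individually determined and increases with age", and that suPAR is associated with chronic diseases.
- Under Data Collection and Monitoring, staff are blinded to the measurements until the study ends.
- Under Sample size and predefined statistical analysis plan, the single regression sentence relates ASA class, suPAR and CRP to postoperative complications. It does not name the composite.

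**The concern.** A bed booked before the operation is a triage decision taken on preoperative information. It is not something that happened to the patient afterwards. If the stay is uneventful, the composite still records an event, and that event is neither a complication nor a death.

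The effect on a comparison by suPAR group depends on who gets the booked beds. suPAR itself cannot drive booking: staff are blinded, and the first sample is drawn only on arrival in the operating room. Age and chronic disease could influence both. If booked beds are commoner in the high-suPAR group, the composite can show an association that partly reflects preoperative triage. If they are equally common in both groups, they add non-informative events and dilute a true association.

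**Working it through.** The plan gives no figure to reproduce here. Its sample size of 100 is built on a suPAR difference of 0.50 between groups, not on the composite, and it states neither an event rate nor a booking rate. All rates below are therefore assumptions.

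**Model.** Let c be the proportion with a complication or death in a group, and b the proportion of the remaining patients with a booked ICU stay. The observed composite rate is c + (1 − c) × b. The odds ratio (OR) compares high with low suPAR. A booked patient who also has a complication or dies is correctly an event; only uneventful booked stays are misclassified.

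**No true effect, c = 0.20 in both groups**

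| Booked, high vs low | Composite, high | Composite, low | OR |
|---|---|---|---|
| none, or equal | same | same | 1.00 |
| 5% vs 2% | 0.20 + 0.80 × 0.05 = 0.240 | 0.20 + 0.80 × 0.02 = 0.216 | (0.240/0.760) / (0.216/0.784) = 1.15 |
| 10% vs 5% | 0.20 + 0.80 × 0.10 = 0.280 | 0.20 + 0.80 × 0.05 = 0.240 | (0.280/0.720) / (0.240/0.760) = 1.23 |

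If c is 15% instead, the last two ORs become 1.19 and 1.29; if c is 50%, they become 1.06 and 1.11. If the booking pattern is reversed (5% high, 10% low), 1.23 becomes 1/1.23 = 0.81.

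**True effect, c = 0.40 vs 0.20, OR = (0.40/0.60) / (0.20/0.80) = 2.67**

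| Booked, high vs low | Composite, high vs low | OR |
|---|---|---|
| 5% vs 5% | 0.430 vs 0.240 | 2.39 |
| 10% vs 10% | 0.460 vs 0.280 | 2.19 |
| 10% vs 5% | 0.460 vs 0.240 | 2.70 |

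With an assumed 50 patients per group, power for the comparison falls from 59% to 52% with 5% booked in both groups, and to 46% with 10%. In the last row dilution and inflation nearly cancel.

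**Booking that follows real risk.** The tables assume that booking is independent of complications within each group. To relax this, a simulation let one latent risk drive suPAR (correlation 0.6, split at the median), booking (logit slope 1.5, about 9% vs 3% booked) and complications (20% overall). As the slope of complications on that risk rises, the inflation shrinks:

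| Complication slope | OR, complications alone | OR, composite | Ratio |
|---|---|---|---|
| 0.5 | 1.60 | 1.91 | 1.91/1.60 = 1.19 |
| 1.0 | 2.34 | 2.56 | 2.56/2.34 = 1.09 |
| 1.5 | 3.15 | 3.24 | 3.24/3.15 = 1.03 |

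It nearly vanishes when booking and complications depend on risk to the same degree, and persists when complications depend on it only weakly.

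**The case against.** The strongest objection is that the premise is not documented. No section says that ICU beds are booked, and the only postoperative destination described is the PACU. The exclusions (obesity, asthma, renal replacement therapy, severe liver disease, transplant, immune disorders) plausibly remove many of the patients for whom a bed would be reserved. This largely stands, and is why the finding is conditional. It does not remove the point: ASA IV patients remain eligible, and passing through the PACU does not rule out a later booked transfer.

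Second, the written regression concerns postoperative complications, which a booked bed does not enter. This stands too. The composite is nevertheless the declared primary endpoint, so any report of it by suPAR group is exposed.

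Third, ICU use may have been meant as an outcome in its own right. That is possible, but the Aim names only complications and mortality.

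Two stronger readings are tempting, and the documents do not support them:

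- A reader might infer a large spurious association. Booking of 30% vs 10% would give an OR of 2.02 with no true effect, but nothing in the documents supports rates of that order, and the figure needs booking to be independent of complications.
- A reader might infer that booked stays could not be separated later, because booked status is missing from the items listed under Data Collection and Monitoring. That list also omits ICU admission, complications and death, which are endpoints. It is plainly not exhaustive and says little about the form itself.

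**Conclusion.** The concern holds in conditional form. As written, the primary endpoint would misclassify an uneventful booked ICU stay as an event, and nothing in the documents prevents this. If the site books no beds, there is no distortion. It would be wrong to conclude that the study's results are biased: whether bias exists, and in which direction, depends on local booking practice, which is not described.

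At modest assumed booking rates the effect is small to moderate: a null OR of 1.15 to 1.23, or a true OR of 2.67 diluted to between 2.39 and 2.19. These figures rest on 20% complications in the low-suPAR group and on independence of booking and complications within group. A broad complication definition would shrink the effect. The secondary definition is broad ("resulting in 22 possible postoperative complications"), but the primary endpoint does not say whether it uses it. That the plan states no model for the composite is a separate point. This one is a cheap improvement, not a fatal flaw.

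**What to change.** 1. Define the component as ICU admission or readmission not booked before the start of surgery.
2. Record booked-bed status before surgery on the data collection form. The plan already commits to such a form: "Data analysis will be based on predefined data points on a prospective data collection form".
3. Report complications, unbooked ICU admission, booked ICU admission and death separately by suPAR group.
4. Keep the any-ICU composite as a sensitivity analysis.

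The cost is one line of wording, one tick-box and one table. No patient's care changes. There are two downsides.

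- **Fewer events.** Per 100 patients, 100 × (1 − c) × b no longer count. With c = 0.20 and 2% to 10% booked, that is 1.6 to 8.
- **Some masking.** ICU need that arises in a patient already in a booked bed is captured only through the complications or death components. Suppose 5% of patients without a complication have such need in both groups, with booking of 10% vs 5% and no true effect. The restricted rates are 0.20 + 0.80 × 0.05 × 0.90 = 0.236 and 0.20 + 0.80 × 0.05 × 0.95 = 0.238, so the OR is (0.236/0.764) / (0.238/0.762) = 0.99. This opposite bias is much smaller than the 1.23 it replaces, but it is the reason to report both definitions and the components.
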